## **10. Safety**

The population used for safety analyses of the double-blind treatment phase will be the Safety Set (SS) and of the extension phase will be the EPS. All safety assessments will be listed by treatment group and patient ID. Visit-wise assessed safety parameters will be listed by treatment group, patient ID and visit/timepoint. Unscheduled assessments will be flagged and presented in listings. Adverse events will be listed by treatment group, patient ID, start date/time and stop date/time.

### **10.1. Extent of Exposure**

Number and percentage of patients who received the first 6 cycles of study treatment (i.e., completed study treatment) of the double-blind treatment phase and who received only 5, 4, 3, 2, or 1 cycles will be presented by treatment group and overall. Additionally, the number and percentage of patients who received all 6 cycles of study treatment within the double-blind extension phase (TP7 to TP12) and who received only 11, 10, 9, 8, or 7 cycles will be presented by treatment group and overall for the EPS. The dose applied in each treatment period TP1 to 12 will be summarised by SEL-212 group.

Number and percentage of patients who met the stopping rules will be summarized by treatment group, overall SEL-212 and treatment period. The percentage will be plotted versus treatment period by treatment group for the treatment phase on the SS. Additionally, the percentage will be plotted versus treatment period by treatment group for the whole study (treatment phase and extension phase) on the EPS.

### **10.2. Treatment Compliance**

Treatment compliance will be calculated for the two active components SEL-110.36 and SEL-037 for each SEL-212 treatment group separately in a first step. In a second step these compliances will be pooled to one overall compliance for each SEL-212 treatment group.

For each component SEL-110.36 and SEL-037 the following will be calculated for each patient in each of the SEL-212 treatment groups:

- 1) For each treatment period i and patient j: Compliance of SEL-xx in period i =  $100\% \times (\text{total volume infused in period i}) / (\text{total volume planned in period i})$ .
- 2) For each treatment period i and patient j: Overall compliance in period i =  $(\text{compliance of SEL-110.36 in period i} + \text{compliance of SEL-037}) / 2$ ;
- 3) Mean overall treatment compliance of patient j = Sum of overall compliances in all applied treatment periods of patient j divided by the number of applied treatment periods.

The overall treatment compliance for each period and the mean overall treatment compliance for the double-blind treatment phase (TP1 to 6) and the double-blind extension phase (TP7 to 12) will be summarized and presented by SEL-212 treatment group on the SS and EPS, as appropriate.

Additionally the volume and infusion duration (defined as stop time of infusion – start time of infusion) in each treatment period will be summarized for each SEL-212 treatment group and for placebo.

### **10.3. Adverse Events / Adverse Drug Reactions**

All adverse events (AEs) will be coded using the most recent MedDRA Version. All AEs will be summarized by system organ class (SOC) and preferred term (PT) for each treatment group, for overall SEL-212 and in total for the whole study, but also for the double-blind treatment phase and the double-blind extension phase separately. A treatment-emergent AE (TEAE) is an AE that starts or worsens at any time after

This document is confidential.

initiation of study drug on Day 0 of Treatment Period 1 until the End of Study Visit (30 days after completion of the last dose of study drug). TEAEs will be further classified as treatment-emergent for the double-blind treatment phase (these are all AEs which start prior to the first dose in the extension phase) and as treatment-emergent for the double-blind extension phase (these are all AEs which start after the first dose in the extension phase or increase in intensity after start of study drug in the extension phase). Additional analysis will be performed on a subset of infusion reactions (this is a study drug-related AE that occurs within 1 hour after completion of study drug infusion) that fulfil the criteria of an Allergic Reaction/Hypersensitivity according to the Rheumatology Common Toxicity Criteria, version 2.0.

Following AEs are considered as AEs of special interest (AESIs): gout flares, infections, malignancies, viral infections, interstitial lung disease, stomatitis, infusion-related reactions including anaphylaxis, thrombosis (e.g., deep venous thrombosis, pulmonary embolism), and the following laboratory tests, if deemed clinically significant by the PI: hyperlipidemia, worsening of renal function tests, proteinuria, and leukopenia.

An overall summary will be provided of the number and percentage of patients reporting AEs, TEAEs, treatment-related (possibly related and related) TEAEs, serious TEAEs, treatment-related serious TEAEs, AESIs, infusion reactions (this is a study drug-related AE that occurs within 24 hours after initiation of study drug infusion), infusion reactions (this is a study drug-related AE that occurs within 1 hour after completion of study drug infusion) that fulfil the criteria of an Allergic Reaction/Hypersensitivity according to the Rheumatology Common Toxicity Criteria, version 2.0. Any gout flare which occurs within 24 hours after initiation of study drug infusion will be listed as a gout flare and not as an infusion reaction. TEAEs leading to study drug withdrawal and TEAEs leading to death. In the overall summary, additionally, the number and percentage of patients with at least one severe TEAE, with at least one moderate TEAE but no severe TEAE and with only mild TEAEs will be provided. The overall summary will be provided for all AEs in the study and for the AEs in the double-blind treatment phase on SS. Additionally, the overall summary will be provided for the whole study and for each period on EPS.

The number and percentage of patients with TEAEs / treatment-related TEAEs / serious TEAEs / AESIs / TEAEs leading to study drug withdrawal/ will be summarized by SOC and PT for each treatment group. TEAEs will also be summarized by SOC and PT for maximum intensity and maximum causality for each treatment group. All defined summaries will be provided for all TEAEs in the study and for the TEAEs in the double-blind treatment phase on SS. Additionally above defined summaries will be provided on the EPS for the whole study and for each period.

Exposure-adjusted event rates based on i) patients and also based on ii) events by treatment group, overall SEL-212 and total will be provided for patients with at least one related TEAE, at least one SAE, at least one TEAE of special interest and also for specific TEAEs of special interest. For SAEs and AESIs that occur in  $\geq 2\%$  of individuals, as well as the most common TEAEs, the rate difference of exposure-adjusted event rates between the two treatment groups together with the 95% confidence interval will be provided; this will also be presented for the two treatment groups combined vs. placebo.

i) Exposure –adjusted event rate in treatment group A based on patients = Number of all patients with at least one event in treatment group A / Total sum of the treatment exposure time of all patients in treatment group A.

ii) Exposure –adjusted event rate in treatment group A based on events = Number of all events in treatment group A / Total sum of the treatment exposure time of all patients in treatment group A.

This document is confidential.

Listings of TEAEs and non-TEAEs will be provided. The treatment-emergent AEs for the double-blind treatment phase and for the double-blind extension phase will be flagged, respectively.

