5.4 Impact on Quality of Life

One longitudinal study in this patient population reports that approximately 70% of patients with chronic refractory gout have at least 1 tophus and an average of 7 flares per year. In a separate study of chronic refractory gout, patients self-reported more than 60% of these flares as crippling ([Brook 2010](#)). Symptoms of pain, limited mobility, and disability are debilitating and deeply affect physical function and emotional and social functioning, and disease severity correlates with a marked compromise in quality of life ([Strand 2012](#), [Becker 2009](#)).

The relationship between self-reported quality of life and disability and disease severity have been evaluated in multiple clinical studies. Over 100 subjects with chronic refractory gout evaluated using the Medical Outcomes Study Short Form-36 assessment, and results revealed that patients with chronic refractory gout have significantly lower subscales analogous to those of 75-year old individuals ([Becker 2009](#)). Specifically, disease severity, as characterized by number of flares in the past year, number of tender or swollen joints, or presence of tophi, significantly correlates with worse quality of life scores in all areas, which include bodily pain, general health, mental health, physical functioning and vitality. Subjects with comorbidities experienced worse physical functioning ([Strand 2012](#)).

There is also evidence that gout affects workplace productivity, as studies in patients with chronic, refractory gout self-report work absences due to flares, losing 25.1 workdays on average per year.

Another study specifically found employees with gout missed 4.56 more days of work per year than those without gout ([Edwards 2011](#)).

Hospitalizations with a principal diagnosis of gout has steadily increased over the past 2 decades ([Lim 2016](#)). In contrast, hospitalizations due to rheumatoid arthritis (RA) has dramatically decreased over this same time period correlating with the development of effective biologic drugs to treat RA. In 2005, the number of hospitalizations due to gout exceeded the number of hospitalizations due to RA, and this gap has steadily increased. Hospitalization costs for gout and RA show a similar trend. Similarly, general population studies have shown a substantial reduction in premature death in RA patients but not in gout patients ([Rai 2016](#)). The findings likely reflect lack of effective therapies for severe gout.

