7.7 Benefits and Risks

Chronic gout refractory to conventional therapy is a rare and serious condition associated with increased mortality rate and significantly decreased quality of life and for which there are very limited treatment options. Data from the Phase 2 study SEL-212/201 provide preliminary clinical evidence demonstrating that SEL-212 is a substantial improvement over available therapy:

- Substantially increased percentage of patients that maintain control of sUA while on therapy
- Substantially reduced gout flare rate during therapy
- Substantially reduced risk of infusion reactions
- More convenient to and greater compliance by patients because of once monthly therapy
- Acceptable safety at the dose to be studied in this Phase 3 study
- Potential to re-treat patients after a gap in therapy (> 1 month) because of the mechanism of action of SEL-212

SEL-212 has the potential to be an unprecedented safe and effective treatment option for patients for which other treatment options are inadequate. The overall balance between benefits and risks appears acceptable for the Phase 3 study of SEL-212 in the intended population of patients with chronic gout refractory to conventional therapy.

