10.6 Premedication

10.6.1 Gout Flares (Prophylaxis and Treatment)

All patients that are expected to be randomized will be premedicated for gout flare prevention. The regimen will begin at least 7 days prior to the first dosing of study drug and continue for as long as the patient is participating in the clinical study.

Patients not already taking colchicine will receive colchicine 1.2 mg as a single loading dose followed by 0.6 mg QD for the remainder of participation in the trial. If the patient cannot tolerate the loading dose level of 1.2 mg, then the patient will initiate and maintain colchicine at 0.6 mg per day. If the patient cannot tolerate the loading dose level of 0.6 mg, then the patient will initiate and maintain colchicine at 0.3 mg per day.

Patients with a documented medical reason that describes a contraindication to colchicine will receive ibuprofen 600 mg TID or an equivalent NSAID unless the patient has a contraindication to NSAID. At the discretion of the Investigator, a proton pump inhibitor may be prescribed with the NSAID as gastric prophylaxis. Patients with documented medical reasons that describe contraindications to both colchicine and NSAIDs will receive no premedication for gout flare.

Patients who began receiving a NSAID as gout flare prevention medication due to a contraindication to colchicine should continue to receive the NSAID during study participation.

As gout flares are expected to occur despite preventative premedication, incidents of gout flare are to be recorded as an AE and treated at the discretion of the Investigator to provide adequate patient care.

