- Infusion Reactions (an AESI) will be reported to Parexel Safety in the same manner as SAEs using the same form but ticking the AESI box rather than the SAE box.

Adverse events of special interest (AESI) will be recorded specifically for occurrences of: gout flares, infections, malignancies, viral infections, interstitial lung disease, stomatitis, infusion-related reactions including anaphylaxis, thrombosis (e.g., deep venous thrombosis, pulmonary embolism), and the following laboratory tests, if deemed clinically significant by the PI: hyperlipidemia, worsening of renal function tests, proteinuria, and leukopenia.

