13.5.2 Adverse Events / Adverse Drug Reactions

All AEs will be coded and grouped into Preferred Terms (PT) by System Organ Class (SOC), using the most recent MedDRA Version. All AEs will be summarized by SOC and PT.

Summaries by each treatment group for the whole study (i.e., double-blind treatment phase and double-blind extension phase) and for the double-blind treatment phase will be provided on the Safety Set overall and by SOC and PT with the number and percentage of patients reporting TEAEs, serious TEAEs, treatment-related TEAEs, AEs of special interest (AESIs), infusion reactions (this is a study drug-related AE that occurs within 24 hours after initiation of study drug infusion), TEAEs leading to withdrawal and TEAEs leading to death. Additional analysis will be performed on a subset of infusion reactions (this is a study drug-related AE that occurs within 1 hour after completion of study drug infusion) that fulfil the criteria of an Allergic Reaction/Hypersensitivity according to the Rheumatology Common Toxicity Criteria, version 2.0. In the overall summary, additionally, the number and percentage of patients with at least one severe TEAE, with at least one moderate TEAE but no severe TEAE and with only mild TEAEs will be provided. Similar summaries will be produced for the subset of patients continued into the double-blind extension phase (i.e., on the EPS) considering the whole study but also separately for each treatment phase.

The number and percentage of patients with TEAEs / serious TEAEs / treatment-related TEAEs / TEAEs of special interest and TEAEs leading to withdrawal will be summarized by SOC and PT for each treatment group and overall for the whole study and for the double-blind treatment phase on the Safety Set. Similar summaries will be produced for the subset of patients continued into the double-blind extension phase (i.e., on the EPS) considering the whole study but, also separately for each treatment phase.

Event rates by treatment group and overall will be provided for patients with at least one related TEAE, at least one SAE, and at least one TEAE of special interest. Additionally, the rate difference with 95% confidence interval comparing each SEL-212 treatment group to placebo as well as comparing the integrated SEL-212 arms to placebo will be provided.

TEAEs will also be summarized by maximum intensity and relationship to study drug.

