### **4.2. Secondary Efficacy Endpoints**

#### Key Secondary Endpoints:

Each of the two active treatment groups, SEL-212A and SEL-212B, are compared to placebo with regards to the following key secondary endpoints:

- Reduction of mean sUA as computed by subtracting the Baseline sUA level from the mean sUA during Treatment Period 6
- Percent reduction of mean sUA as computed by subtracting the Baseline sUA level from the mean sUA during Treatment Period 6
- The change from Baseline to Day 28 of Treatment Period 6 in the physical summary score of the Short Form Health Survey (SF-36)
- In patients with tophi at Baseline, the percentage of patients with at least PR (as best response) in overall tophus response evaluation until Day 28 of Treatment Period 6
- The percentage of patients who achieve and maintain reduction of sUA < 6 mg/dL for at least 80% of the time during Treatment Period 6 by Day 28, in the subset of patients with tophi at baseline
- The change from Baseline to Day 28 of Treatment Period 6 in number of tender joints
- The change from Baseline to Day 28 of TP6 in the total score of the Health Assessment Questionnaire (HAQ-DI)
- Gout flare incidence during Treatment Periods 1-6
- Gout flare incidence during Treatment Periods 1-3

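### The composite of any adverse event of special interest counts gout flare, an efficacy outcome, so it dilutes and can cancel an excess of other such events; add a flare-free line

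*SAP*

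**What the plan says.** SAP 10.3 opens its list of adverse events of special interest (AESIs) with gout flare: "Following AEs are considered as AEs of special interest (AESIs): gout flares, infections, malignancies, viral infections, interstitial lung disease, stomatitis". Protocol 12.2.1.5 has the same list: "Adverse events of special interest (AESI) will be recorded specifically for occurrences of: gout flares, infections, malignancies, viral infections". Protocol 10.6.1 makes every flare an adverse event: "As gout flares are expected to occur despite preventative premedication, incidents of gout flare are to be recorded as an AE".

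The same event is an efficacy outcome. SAP 4.2 lists among the key secondary endpoints "Gout flare incidence during Treatment Periods 1-6". Protocol 7.7 counts among the phase 2 findings "Substantially reduced gout flare rate during therapy", a claim made against available therapy rather than placebo.

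Protocol 13.5.2 plans event rates for patients with "at least one related TEAE, at least one SAE, and at least one TEAE of special interest". Its next sentence adds a rate difference with a 95% CI for each SEL-212 arm, and for the two arms pooled, against placebo. SAP 10.3 plans the percentage of patients with AESIs and two exposure-adjusted rates: patients with an event over total treatment exposure, and all events over the same denominator. Neither document plans an AESI composite without flares.

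SAP 10.3 also plans rates for specific AESIs, rate differences for AESIs reaching 2% of individuals, AESI tables by system organ class and preferred term, and separate infusion-reaction rows. A flare within 24 hours of the start of infusion is kept out of those infusion-reaction rows.

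**The concern.** An AESI composite is read as a summary of overall toxicity. Here it also rises and falls with disease control. If flares are frequent, many patients already count as having an event, and an excess of infections, stomatitis, infusion reactions or laboratory toxicity moves the composite little. If SEL-212 lowers flares, efficacy enters with the opposite sign to toxicity and the composite can show no difference, or favour SEL-212, while the other AESIs are more frequent on drug. SAP 10.3 already separates flares from infusion reactions. The same separation is missing one level up.

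**Working it through.** **Figures in the documents.** Neither document gives an expected AESI or flare percentage for this trial. The nearest is the interim AESI composite from study SEL-212/202 (Protocol 7.6.3.2.2), which included flares: 33/83 = 39.8% on SEL-212 and 24/86 = 27.9% on the comparator. Both reproduce. The difference is +11.9 points (95% CI -2.3 to +26.0). Both arms were active drugs and only 27 of 170 subjects had completed, so this is neither a placebo estimate nor a six-month value.

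**How many patients would flare?** Protocol 5.4 cites patients who "have at least 1 tophus and an average of 7 flares per year". Over the 168-day treatment phase that is 7 × 168/365.25 = 3.22 expected flares. P(at least one) is 1 − exp(−μ) under a Poisson model and 1 − (1 + μ/k)^(−k) under a negative binomial model with shape k. The values of k and the lower annual rates are assumptions.

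| Flares per year | Poisson | Negative binomial |
|---|---|---|
| 7 | 96% | 76% (k=1), 63% (k=0.5), 48% (k=0.25) |
| 2 | 60% | 32–53% (k=0.25 to 2) |
| 1 | 37% | 23–34% (k=0.25 to 2) |

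**Patient-based composite.** Let f be the flare risk and t the risk of any other AESI, taken as independent. Then P(any AESI) = 1 − (1−f)(1−t). With equal f, the difference between arms is (1−f) times the true difference in t. Assume t = 40% on SEL-212 and 20% on placebo.

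| Flare risk, SEL-212 / placebo | SEL-212 | Placebo | Difference |
|---|---|---|---|
| Flares excluded | 40.0% | 20.0% | +20.0 |
| 40% / 40% | 1 − 0.60×0.60 = 64.0% | 1 − 0.60×0.80 = 52.0% | +12.0 |
| 76% / 76% | 1 − 0.24×0.60 = 85.6% | 1 − 0.24×0.80 = 80.8% | +4.8 |
| 30% / 40% | 1 − 0.70×0.60 = 58.0% | 52.0% | +6.0 |
| 60% / 76% | 1 − 0.40×0.60 = 76.0% | 80.8% | −4.8 |

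The sign reverses when the SEL-212 flare risk falls below 1 − (1−f_placebo)(1−t_placebo)/(1−t_SEL). That is 20.0% for placebo flaring of 40%, 50.7% for 63% and 68.0% for 76%. With the smaller assumption t = 30% v 20%, the thresholds at 40% and 76% placebo flaring are 31.4% and 72.6%, so a smaller excess is cancelled more easily.

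For crude proportions at 40 v 40 patients, the chance that a two-sided 5% comparison detects the assumed excess is 50% with flares excluded, 19% at 40% flaring and 8% at 76%.

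**Event-based rate.** This rate cannot saturate, but flare counts add to it directly. Suppose non-flare AESI events double from 0.3 to 0.6 per patient with equal exposure (assumed). The extra 0.3 is cancelled by a flare reduction of 0.3/3.22 = 9% at 7 flares per year. At 2 per year (2 × 168/365.25 = 0.92 flares) it takes 0.3/0.92 = 33%.

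**Error in the other direction.** Suppose 76% have an AESI in both arms. Let placebo exposure be 168 days. On SEL-212 let 45% complete (the sample-size responder rate, borrowed for illustration) and the rest stop at 56 days: 0.45×168 + 0.55×56 = 106.4 days. The patient-based rate is then 0.76 × 365.25/168 = 1.65 per patient-year on placebo and 0.76 × 365.25/106.4 = 2.61 on SEL-212. That is 165 v 261 per 100 patient-years with no difference in risk.

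**Rare AESIs.** If the 2% threshold is taken over all 120 patients, an event in one or two patients (2/120 = 1.7%) gets no difference of its own and enters a comparison only through the composite. The SAP does not state the denominator; within an arm, 1/40 = 2.5% would qualify.

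**The case against.** The strongest reply is that most of the protection is already planned. Specific-AESI rates, differences for AESIs reaching 2%, tables by organ class and preferred term, and separate infusion-reaction rows all sit in SAP 10.3. SAP 9.3.3 reports patients with flares on their own. An excess in one common component would be seen. This stands, and it confines the point to the composite line and to AESIs too rare for their own difference.

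A reader might also infer that the composite saturates because most patients will flare. The documents do not support that. The 96% figure takes a background rate, ignores the flare prophylaxis that Protocol 10.6.1 requires unless contraindicated, and assumes no variation between patients. Protocol 10.6.1 expects flares but gives no proportion, and the one observed composite that included flares was 28–40%.

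Nor is the composite powered to show an overall toxicity excess. The sample size in Protocol 13.1 rests on the primary efficacy endpoint alone, and the safety comparisons are descriptive.

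Finally, SAP 10.3 does not clearly attach its rate difference to the composite; its wording fits individual AESIs better. It also speaks of a difference between two treatment groups in a three-arm trial, and then of those two groups combined against placebo. Read literally, the first difference would compare SEL-212A with SEL-212B. Protocol 13.5.2 is clearer, since its difference directly follows the composite. This objection narrows what the SAP can be said to plan, but it also shows that the wording needs repair.

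**Conclusion.** The point holds in a limited form. The any-AESI percentage and rates, and the difference in Protocol 13.5.2, pool an efficacy outcome with toxicity, and no flare-free counterpart is planned. A real excess of other AESIs is diluted, and it can be cancelled or reversed if SEL-212 lowers flares. Under the assumed 40% v 20%, the 20-point excess appears as anything from +12.0 to −4.8 points across the flare scenarios shown. Those figures rest on assumed toxicity and flare risks and on independence. The event-based result rests on assumed event counts and equal exposure. The bias need not hide toxicity: shorter SEL-212 exposure can create a false excess in the patient-based rate. Type I error, sample size and patient management are unaffected.

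**What to change.** In SAP 10.3:

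- Add a line for patients with at least one AESI other than gout flare to the AESI percentage, to both exposure-adjusted rates and to the rate difference with 95% CI. State that this is the main line for judging overall AESI toxicity.
- Show gout flare on its own row beside it, and keep the composite including flare so that the protocol's analysis is still reported.
- Name the comparisons: SEL-212A v placebo, SEL-212B v placebo, and combined SEL-212 v placebo. State that the difference applies to the composite lines as well as to individual AESIs.

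The cost is one extra row per table, from data already collected and coded. Protocol section 13 lets the SAP add exploratory analyses, so no protocol amendment is needed. The added line does not remove the exposure artefact, so the crude percentages should be read alongside the patient-based rates.

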12.2.1.5 Infusion Reactions / Adverse Events of Special Interest

A study drug-related AE that occurs within 24 hours after initiation of study drug infusion will be assessed as an infusion reaction. An infusion reaction suspected to be anaphylaxis will be assessed according to the clinical criteria for the diagnosis of anaphylaxis based on the National Institute of Allergy and Infectious Diseases (NIAID) / Food Allergy & Anaphylaxis Network (FAAN) Symposium criteria. ([Sampson 2006](#)).

Infusion reactions will be managed and treated as described below. In addition to premedication with antihistamines and steroids ([Section 10.6.2](#)), the following steps will be implemented in this protocol to either reduce the risk of infusion reactions or manage infusion reactions.

- Patients with prior exposure to uricase therapy will be ineligible
- Patients with a history of anaphylaxis or severe allergic reactions, history of severe atopy, angioedema, or previous infusion reactions will be excluded from the trial.

 Selecta Biosciences	PHASE 3 STUDY: SEL-212/301 VERSION: 6.1	EFFECTIVE DATE 15 DECEMBER 2022
--	--	------------------------------------

- Study drug will be administered at controlled rates only in a healthcare setting and by healthcare providers sufficiently equipped and prepared to manage infusion reactions including anaphylaxis.
- In case of infusion reaction, sites will perform specific assessments as specified in the Study Operations Manual.
- Each patient will be observed for infusion reactions after dosing of study drug in the clinic for approximately 4.5 hours from the start of study drug infusion. Patients will be informed about the signs or symptoms of infusion reactions and will be instructed to notify the Investigator immediately if they believe they are experiencing a reaction.
- Each patient shall remain for a minimum of 1 hour after the completion of infusion of study drug for a period of safety observation.
- All patients will be contacted approximately 24 hours after infusion to determine whether any infusion reaction AEs occurred.
- Patients who experience an infusion reaction will be contacted approximately 24 hours after the event as follow-up.
- Only sites with immediate capability to appropriately respond to a reaction of this severity will be allowed to participate in the trial to reduce the risk to any patient.

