13. STATISTICS

Details of the statistical methods outlined in the protocol for this study, including the hierarchical ordering of the secondary endpoints, will be documented in a Statistical Analysis Plan (SAP), which will be finalized prior to database lock. The SAP may add additional exploratory analyses; modifications to the planned analyses will be identified as such in the final SAP.

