## **12. Deviation from Analyses Planned in Protocol**

The key secondary endpoints for gout flare will be analyzed by ANOVA instead of ANCOVA as specified in the protocol, as adjustment for baseline is not possible given gout flare incidence is not assessed at baseline.

This document is confidential.

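### SAP 10.3 narrows the protocol's definition of an infusion reaction by excluding gout flares, and SAP Section 12 does not declare the change

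*SAP*

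**What the plan says.** **Protocol, definition.** Section 12.2.1.5: "A study drug-related AE that occurs within 24 hours after initiation of study drug infusion will be assessed as an infusion reaction". Section 13.5.2 carries the same definition into the planned safety analysis, naming among the events to be summarised "infusion reactions (this is a study drug-related AE that occurs within 24 hours after initiation of study drug infusion". Neither section makes an exception for gout flares.

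**Protocol, status of flares.** Section 10.6.1: "incidents of gout flare are to be recorded as an AE". A flare that the investigator attributes to study drug, and that falls within 24 hours of infusion start, therefore meets the protocol definition.

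**SAP.** Section 10.3 repeats the 24-hour definition in its overall adverse event summary. It then adds that any gout flare in that window "will be listed as a gout flare and not as an infusion reaction". The same section keeps flares as a category of special interest ("Following AEs are considered as AEs of special interest (AESIs): gout flares, infections") and indicates what it counts as drug-related ("treatment-related (possibly related and related) TEAEs").

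**Declaration of changes.** Protocol Section 13 says that "modifications to the planned analyses will be identified as such in the final SAP". SAP Section 12 contains one item: "The key secondary endpoints for gout flare will be analyzed by ANOVA instead of ANCOVA as specified in the protocol". Infusion reactions are not mentioned there.

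**The concern.** The protocol commits to one count and the SAP produces a narrower one, without saying that anything has changed. SAP 1.1 (21 February 2023) is later than protocol 6.1 (15 December 2022), so the SAP was not written against a future definition.

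Three things are at stake:

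- **Two counts.** Under protocol 12.2.1.5, sites send infusion reactions to the safety group on the form used for serious events, using the protocol definition. The tables will use the SAP definition, and no reconciliation is planned.
- **Prominence.** Infusion reactions are a named event of special interest, and protocol 7.7 puts a lower risk of them among the arguments for the product.
- **Scope.** The exclusion is one sentence inside the paragraph on the overall summary, and it speaks of listing. The SAP does not say whether it also governs the rates and rate differences for events of special interest later in the same section.

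**Working it through.** Neither document gives an expected infusion-reaction rate or a rate of flares within 24 hours, so there is no planned figure to reproduce. The check is mainly a comparison of definitions.

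**1. Side by side**

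| Event within 24 h of infusion start | Protocol 12.2.1.5 and 13.5.2 | SAP 10.3 |
|---|---|---|
| Drug-related event other than a flare | Infusion reaction | Infusion reaction |
| Drug-related gout flare | Infusion reaction | Gout flare only |
| Gout flare not drug-related | Not an infusion reaction | Gout flare only |

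The definitions differ in the second row only. There the SAP moves events out of the infusion-reaction count and moves none in. The count can fall or stay the same, but cannot rise.

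**2. Size per patient.** A patient leaves the count only if a drug-related flare in the window was that patient's sole qualifying event. With about 40 patients per arm:

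- one arm: 1/40 = 2.5 percentage points
- both SEL-212 arms pooled: 1/80 = 1.25 percentage points

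These figures are for the crude proportion of patients. SAP 10.3 also plans exposure-adjusted rates based on events. If the exclusion governs those, each reclassified flare lowers the event count, even in a patient who has another infusion reaction.

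**3. Reporting threshold.** SAP 10.3 gives rate differences for events of special interest seen in at least 2% of individuals. Across 120 patients that is 0.02 × 120 = 2.4, so 3 patients. A few reclassifications could matter at that margin.

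**4. Does the between-arm direction follow?** For illustration only, take the background rate of 7 flares per year from protocol 5.4, spread evenly over time, with six one-day windows:

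- expected flares per patient in the windows: 7/365.25 × 6 = 0.115
- proportion with at least one: 1 − exp(−0.115) = 10.9%, about 4.3 patients in 40

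Assume that 25% of these flares are judged drug-related and that no patient has another qualifying event. The placebo proportion then falls by 1 − exp(−0.115 × 0.25) = 2.8 points. For SEL-212, multiply the exponent by an assumed active-to-placebo ratio of flares in the window:

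| Ratio (assumed) | Fall, SEL-212 | Fall, placebo | Difference in fall |
|---|---|---|---|
| 0.5 | 1.4 | 2.8 | −1.4 |
| 1 | 2.8 | 2.8 | 0 |
| 2 | 5.6 | 2.8 | +2.8 |
| 3 | 8.3 | 2.8 | +5.4 |

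Differences are taken before rounding. If no flare is judged drug-related, every entry is zero. The sign depends entirely on a ratio that the documents do not give.

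**The case against.** **Nothing is lost.** Flares remain an event of special interest with their own rates, flare incidence is a key secondary endpoint, and adverse events are listed with start times. This stands: the flares are reclassified, not dropped. However, no planned summary table isolates drug-related flares within 24 hours. A reader of the tables cannot rebuild the count that the protocol specified.

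**The two are distinct conditions.** Both documents list gout flares and infusion-related reactions as separate events of special interest, so the SAP may only be assigning an event to one of two existing categories. This is a fair reason for the exclusion, and the flare-excluded line is worth showing. It does not remove the need to declare a rule that overrides the wording of 12.2.1.5 and 13.5.2.

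**It may be declared elsewhere.** The SAP's revision history was not available for this check, so a mention there cannot be ruled out. Section 12 is still where the SAP puts departures from the protocol.

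**A stronger reading.** A reader might infer that the exclusion acts mainly in the SEL-212 arms and so favours the product. The documents do not support this:

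- They give no flares within 24 hours by arm.
- Investigators judge relatedness blind, so placebo flares can also be called drug-related.
- The one statement on flare rates under SEL-212 (protocol 7.7, from Phase 2, against available therapy) says they are reduced.
- The stopping rule requires a post-infusion uric acid below 2.0 mg/dL in Treatment Period 1. Placebo patients are not expected to reach that, so they may receive more infusions and have more 24-hour windows.

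The illustrative flare rate is also a background figure. It does not reflect the trial's flare prophylaxis or the steroid premedication before each infusion.

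**Conclusion.** The concern holds as a mismatch of definitions that has not been declared. The SAP as written does not produce the infusion-reaction count that the protocol specifies. The effect on that count is zero or downward: 2.5 percentage points in an arm of 40 for each patient whose sole qualifying event was a drug-related flare, or 1.25 points in the pooled 80. How many such patients there will be is unknown, because it depends on how often investigators attribute early flares to study drug. The direction of any between-arm shift is also unknown, so a claim of bias towards SEL-212 should not be made. Infusion reactions are outside the confirmatory testing hierarchy, so no efficacy conclusion is affected.

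**What to change.** In SAP 10.3:

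1. Tabulate infusion reactions by the protocol definition, with drug-related gout flares within 24 hours included, as the protocol-specified line.
2. Add a second line that excludes gout flares. Show both lines by arm and for each planned rate difference, including pooled SEL-212 against placebo.
3. State which outputs the exclusion governs: the overall summary, the special-interest tables, the exposure-adjusted rates, or only the listings.

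In SAP Section 12, declare the exclusion and give the reason for it.

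The cost is one extra row in the affected tables and a sentence or two of text. The downside is that the protocol-defined rate may be slightly higher than the flare-excluded one. No new data are needed, since relatedness and start times are already collected.
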